All participants will be patients whose response to prior therapies has been partially successful, but limited, and whose disease state and current course represent risk for eventual refractoriness but who have not yet become fully refractory. As defined in detail below, under International Headache Society (IHS) guidelines all of these patients will be classified as "episodic" or acute. None will be classified as "chronic." In assessing the effectiveness of the SNS CVS-M Device, the Pivotal Study will consider both (1) a patient's number of Headaches as well as (2) the severity of each and of all of those Headaches. The current design path involves evaluating those two disease factors both separately and on a blended basis. The primary endpoint is based on a traditional measure with which both the FDA and the medical profession are quite familiar: outcomes data collected during the Treatment Period vs. baseline data from the Pre-Treatment Baseline Period, focusing on comparative number of Migraine Headache Days. Additionally, the concept of blending those two disease measures into one quantitative assessment will be introduced: a Total Monthly Headache Pain score. As defined below, that Monthly measure will be the cumulative maximal Headache Pain Scores for all Headache Days (days on which the patient's Headache Pain level is one or higher on an eleven-point scale) during the Month in question – thus, a quantitative indication of Total Monthly Headache Pain. Study data can (and will) also be analyzed using other metrics, as described below.

For the Pivotal Study to demonstrate efficacy from SNS CVS-M Device treatments, the therapy must provide prophylactic and/or abortive-response benefits for patients. (However, for clarity, CVS-M is viewed as providing adjunctive prophylactic therapy.) Experience from IRB-approved pilot studies indicates that beneficial preventive effects and diminished incidence and severity of Headaches are achieved through daily CVS-M treatments, but not necessarily beginning immediately upon the first treatment. For that reason, patients will be treated for three Months and only the Headache burden during the last Month will be used for comparison with baseline data.

Description of the Treatment Paradigm and Study

1) Intended Use/Indication for Use

- **Intended Use:** The SNS CVS-M Device is intended to stimulate the vestibular system via external ear canals using controlled thermal waveforms.

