For active-treatment subjects as a group: During the third Month of the Treatment Period, their average total number of Monthly Migraine Headache Days will be lower than their comparable averages derived from the Pre-Treatment Baseline Period.

• Secondary Efficacy Endpoints for the Pivotal Study

- The number of active-treatment subjects having a reduction of 50% or more in Migraine Headache Days during the third Month of the Treatment Period as compared with the Pre-Treatment Baseline Period will exceed the number of placebo-treatment patients having that response rate.
- For active-treatment subjects as a group: During the third Month of the Treatment Period, their average Total Monthly Headache Pain Scores will be lower than their comparable averages derived from the Pre-Treatment Baseline Period.
- For active-treatment subjects as a group: During the third Month of the Treatment Period, their average number of Treated Headaches will be lower than their comparable averages derived from the Pre-Treatment Baseline Period.
- For active-treatment subjects as a group: On average, in comparison with their Pre-Treatment Baseline Period, they will have at the end of the Treatment Period, improvement in scores associated with the Quality of Life and Cognition Assessment measures.

• Safety Endpoint for the Pivotal Study:

The principal safety endpoint for the Study is to verify the absence of material dizziness, with the associated risk of falls, as a consequence of using the active-treatment Device. The Berg Balance test will be used to assess any changes in balance performance as a result of Device usage. Transient nausea and minor dizziness may be experienced by patients, as is sometimes reported in the diagnostic CVS literature, and patients will be trained to verify balance stability after a treatment and before standing up. Previous pilot studies using the Device did not identify nausea or dizziness as side effects attributable to the Device, based on patient self-reporting.

8) Calculating Total Monthly Headache Pain Scores

For each subject the following Total Monthly Headache Pain calculations will be made:

- a. Using the Daily Headache Diary data from the Pre-Treatment Baseline Period, the cumulative Pain Scores for all of the days on which the subject had a Headache during the Month will be calculated; and
- b. For the third Month of the Treatment Period, the cumulative Pain Scores for all of

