the days on which the subject had a Headache during the Month will be calculated.

At the conclusion of the Pivotal Study, Total Monthly Headache Pain score comparisons will be made for each subject: Pre-Treatment Baseline Period vs. the third Month of the Treatment Period. Additionally, such Total Monthly Headache Pain scores for the active-treatment subjects as a group will be compared with those for the placebo-treatment subjects as a group.

9) Statistical Analysis and Pivotal Study Size

As noted above, an experienced, independent and blinded Statistician will be utilized to analyze and summarize the Daily Headache Diaries for all patients. Also, as noted, a blinded Neuropsychologist will analyze and summarize the Quality of Life and Cognition Assessment data, and a Vestibular System Consultant will perform a blinded analysis and summary of the data from the Vestibular Testing Procedures.

Summary of the analytical methodology to be used for the Primary Endpoints

- No prospective stratification: Based on the inclusion and exclusion criteria, there is no medical reason to stratify the Pivotal Study's episodic migraine population.
- **Statistical method**: The Pearson's chi-square test will be used to evaluate the null hypothesis, which is that "There is no difference between the number of Migraine Headache Days (during the third Month of the Treatment Period as compared with the Month during the Pre-Treatment Baseline Period) when comparing subjects treated with the Treatment Device and subjects treated with Placebo Device."

The corresponding alternative hypothesis is that: "There is a reduction in Migraine Headache Days (during the third Month of the Treatment Period as compared with the Month during the pre-Treatment Baseline Period) when comparing subjects treated with the Treatment Device and subjects treated with Placebo Device."

We seek to power the Study so as to reject the null hypothesis and accept the corresponding alternative hypothesis. The following power calculations are based on probabilities from binomial distributions (2-sided test):

- Assumed efficacy metric (response rate): a reduction of 50% or more in Migraine Headache Days with respect to baseline.
- Assumed range of efficacy measured in the placebo arm: 10-15%
- Assumed range of efficacy measured in the treatment arm: 45-55%

Treatment efficacy	Placebo efficacy	Statistical power	Total minimum
			cohort size
45%	15%	80%	72
50%	15%	80%	54
55%	15%	80%	44
45%	10%	80%	50

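### The primary endpoint and null hypothesis are in Migraine Headache Days, but the only named test is a chi-square, which needs a cut: it does not match the hypothesis and, if benefit is spread across patients, it costs power

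*Combined protocol and SAP*

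**What the plan says.** The Background describes the primary endpoint as a familiar measure, "focusing on comparative number of Migraine Headache Days". Section 7 words it for active-treatment subjects only: in the third Month, "their average total number of Monthly Migraine Headache Days will be lower than their comparable averages derived from the Pre-Treatment Baseline Period".

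Section 9 then states a between-arm null hypothesis that begins "There is no difference between the number of Migraine Headache Days", and says that "The Pearson's chi-square test will be used to evaluate the null hypothesis". No other test is named anywhere in the document.

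The power calculation in section 9 is binomial and two-sided. Its metric is "Assumed efficacy metric (response rate): a reduction of 50% or more in Migraine Headache Days with respect to baseline". Six scenarios follow (active 45-55%, placebo 10-15%), each at 80% power, with totals from 32 to 72. The target is 80 patients.

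The between-arm responder comparison also appears in section 7, as the first secondary endpoint: "The number of active-treatment subjects having a reduction of 50% or more in Migraine Headache Days".

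**The concern.** Each patient supplies a count of days out of 28 at baseline and again in Month 3. Section 9 asks whether the arms differ in that count, but a chi-square compares proportions in categories. It can be used only after the counts have been cut, and the one cut on offer is the 50% responder metric.

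That has two consequences. First, the test named as primary appears to be the test of a secondary endpoint, while the primary endpoint as worded (a change within one arm) has no test. Second, the cut discards information. A 49% fall scores the same as a worsening, and a 50% fall the same as complete remission. With 4-14 baseline days (section 2) the cut is also coarse: a patient with 4 days needs to fall to 2 (50%), but a patient with 5 must also fall to 2 (60%).

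At stake are a higher risk of missing a real effect, and a primary analysis with no specified between-arm difference and confidence interval in days per Month.

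**Working it through.** **Inputs.** From section 9: responder rates 45-55% v 10-15%, two-sided test, 80% power, 80 patients. From section 3: equal allocation, so 40 per arm. Alpha is not stated; 5% is assumed.

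**Step 1: the plan's own table.** With the usual two-proportion formula (pooled variance under the null, no continuity correction),

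n per arm = [1.96·√(2·p̄·(1−p̄)) + 0.8416·√(p₁(1−p₁) + p₂(1−p₂))]² / (p₁−p₂)².

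At 45% v 15%, p̄ = 0.30: [1.96·√0.42 + 0.8416·√0.375]² / 0.09 = [1.270 + 0.515]² / 0.09 = 35.4, so 36 per arm and 72 in total. All six rows reproduce exactly (72, 54, 44, 50, 40, 32). This supports the assumed 5% and shows that the table is for an uncorrected chi-square on responders.

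**Step 2: chi-square power at 40 per arm, 45% v 15%.** Normal approximation: Φ[(0.30·√40 − 1.270)/0.612] = Φ(1.02) = 84.7%. Exact binomial enumeration gives 85.2%.

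**Step 3: a comparator that keeps the scale.** The documents give no mean change or SD in days, so a shape must be assumed. If both arms are normal with equal variance and one is shifted, the two responder rates fix the standardised difference: d = z(0.45) − z(0.15) = −0.126 + 1.036 = 0.911. The noncentrality is 0.911·√20 = 4.07, and a two-sided t-test has 98.0% power.

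| Active v placebo | Chi-square, exact | t-test, normal shift | Gain (points) |
|---|---|---|---|
| 45% v 15% | 85.2% | 98.0% | 12.9 |
| 50% v 15% | 93.3% | 99.6% | 6.3 |
| 55% v 15% | 97.5% | 99.9% | 2.4 |
| 45% v 10% | 96.0% | 99.9% | 3.9 |
| 50% v 10% | 98.6% | over 99.9% | 1.4 |
| 55% v 10% | 99.6% | about 100% | 0.4 |

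**Step 4: simulated counts at 45% v 15%.** With baselines of 4-14 days and benefit spread over all active patients, several count models (rounded log-normal ratio, gamma-Poisson, binomial out of 28) gave 91-99.8% for a t-test on change in days and 95-99.8% for ANCOVA, against 84-87% for the chi-square. The gain is about 6-15 points. The very highest figures come from models in which the placebo mean rises by several days, so little weight should rest on them.

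**Step 5: the opposite shape.** Suppose about a third of active patients respond (0.30/0.85 = 35%) and the rest behave like placebo.
- If those patients improve by 70-90%, a t-test or ANCOVA in days has about 67-84% power.
- If their falls are uniform between 50% and 100%, a t-test on percent change has 62-78%.
- If they improve by only about 50%, the analysis in days is again ahead (89-96%).

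The chi-square stays at about 85% throughout.

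**Step 6: a case outside the table.** Section 9 quotes 37% v 12.1% for the supraorbital device trial. At 40 per arm the chi-square has 75.9%. Under the normal shift, d = 0.838, noncentrality 3.75, and the t-test has 95.9%. For the occipital stimulator pair (39% v 6%) the chi-square has 97.0%.

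**The case against.** The document never says outright that the chi-square is applied to the 50% cut. That is an inference, though a strong one: the test needs categories, section 9 gives only one way to form them, and its table is that of a two-proportion test.

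The responder metric is not arbitrary. Section 9 uses it to compare the device with two other devices and with topiramate, and to argue clinical meaning. The definitions name a prophylactic-trial guideline as the principal reference, and its content cannot be checked here. That justifies reporting responders. It does not make a chi-square the test of a hypothesis in days.

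The plan will also report average Migraine Headache Days, and the Background says that other metrics will be analysed. So results in days are not absent. What is missing is a specified between-arm difference with its interval.

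Three stronger readings are tempting, and the documents do not support them:
- A reader might infer that the trial is underpowered. By its own standard it is not: about 85% in the least favourable row and 93-99.6% in the other five.
- A reader might take a loss of about 13 points as a fact. It holds in one row of six, under one assumed shape, and it reverses under another. The documents do not show which shape is likelier.
- A reader might pair the 37% active rate quoted for another device with this plan's 15% placebo rate and report 62% power. That mixes sources; the pair as quoted gives about 76%.

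**Conclusion.** The mismatch holds on the text alone and needs no assumption about data: a within-arm primary endpoint in section 7, a between-arm hypothesis in days in section 9, and a named test that fits only the responder comparison listed as secondary.

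The power cost is real but conditional. In the binding 45% v 15% row it is about 6-15 points if benefit is spread across patients. In the other rows the normal-shift figure is about 0.4-6 points. It becomes a loss for the analysis in days if a minority of patients respond strongly. At 37% v 12.1%, where the chi-square falls below 80%, the contrast is about 76% v 96% under the spread-benefit assumption. All of this assumes two-sided 5%, 40 analysed per arm, and a distribution of days that the plan does not supply.

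This is a matter of consistency, efficiency and margin, and does not make the trial invalid. It should be corrected; confidence in the size of the gain is medium.

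**What to change.** - **Section 7:** reword the primary endpoint as the between-arm difference in Month-3 Migraine Headache Days.
- **Section 9:** make the primary test a two-sided ANCOVA of Month-3 Migraine Headache Days on arm and baseline count. Report the difference in days per 28-day Month with its 95% CI, and state alpha.
- **Responders:** keep the 50% comparison with the chi-square as the secondary endpoint it already is, and say explicitly that the chi-square applies to it.
- **Sample size:** keep 80 patients, relabel the existing table as power for the responder endpoint, and add a power statement for the test in days with an explicitly assumed SD. As a guide, 40 per arm gives 80% power for a standardised difference of about (1.96 + 0.8416)·√(2/40) = 0.63 before baseline adjustment. That is about 1.9, 2.5 or 3.1 days if the SD is 3, 4 or 5 days (illustrative values; the documents give none).

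The cost is wording in two sections, made before unblinding, with no more patients, visits or data. There are two downsides: an SD must be assumed, and some power is lost if benefit is confined to a minority of large responders. The retained responder endpoint would still show that pattern.

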 - o have been diagnosed with migraine with aura
 - have menstrual migraine exclusively

- have been diagnosed with post-traumatic migraine
- o have a history of unstable mood disorder or unstable anxiety disorder
- o use a hearing aid
- have a cochlear implant
- have chronic tinnitus
- have temporomandibular joint disease
- have been diagnosed with traumatic brain injury
- o have been diagnosed with neurological disease other than Headaches
- o have a diagnosed vestibular dysfunction
- o abuse alcohol or other drugs
- are experiencing medication overuse Headaches (individuals with respect to whom the Investigator is concerned that analgesic abuse is involved based on the ICHD-II guidelines).
- o are less than 18 years old or greater than 65 years old
- $\circ~$ have had eye surgery within the previous three months or ear surgery within the previous six months
- have active ear infections or a perforated tympanic membrane
- have participated in another clinical trial within the last 30 days or are currently enrolled in another clinical trial
- are using Botox treatments for migraines.
- Though not excluded, patients taking anti-histamines or anti-nausea drugs will be encouraged not to take such medications within four hours prior to a CVS-M treatment. The Investigator should review other medications taken by the patient with properties that mimic anti-nausea or antidizziness drugs as these may reduce responsiveness of the vestibular system to caloric stimulation. Such medications should also be avoided within four hours prior to a CVS-M treatment.

• Withdrawal Criteria

- Subjects must be withdrawn from the clinical trial if any of the following events occur:
 - A subject does not continue to meet Inclusion/Exclusion criteria.
 - A subject is significantly non-compliant with the requirements of the protocol (Investigator decision).
 - A subject becomes pregnant during the trial as evidenced by a positive pregnancy test.
 - The subject develops an illness (Adverse Event) that would interfere with his/her continued participation.
 - The subject is unwilling to continue due to lack of efficacy.

- The subject withdraws his/her consent.
- The Investigator feels that it is the subject's best interest to be withdrawn.
- Scion Neurostim discontinues the study or has achieved the targeted enrollment.

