If the subject is discontinued from the participation in the study for any reason, the Investigator must make every effort to perform all evaluations for the final visit and document the reasons for discontinuation.

• Concomitant Medications

- The use of acute abortive medications for the symptomatic treatment of migraine headache will be allowed during the clinical trial. Subjects may use their usual acute abortive medications, and medications should not be changed during the clinical trial. A Treated Headache will be a Migraine Headache for which a patient has taken an acute abortive medication.
- The patient may be on a single migraine prophylactic as long as the dosage has not been altered within three months of starting the Study and the dosage must not be altered for the duration of the Study. The patient must not have failed on more than two classes of properly administered prophylactic pharmaceutical therapies for migraine headache. Prophylactic medications used to treat other medical conditions may be used, at the Investigator's discretion, if the subject is taking a stable dose for at least three months prior to screening and continues throughout the study.

3) Pivotal Study Size; Randomization

The design size contemplates enrolling up to eighty (80) patients who will successfully follow through to completion of their participation in the Pivotal Study. Half of these patients will be assigned a Treatment Device, and half will be assigned a Placebo Device. Whether a patient is in the treatment arm or placebo arm will be decided randomly based on an assignment within a sealed envelope, which will be opened only by the Pivotal Study coordinator at the relevant Pivotal Study site. The envelopes will be randomized as described below and provided to the participating clinics. A given patient and the Investigator will remain blinded as to the arm to which the patient has been assigned. The assessment of the primary endpoints will be completed by a blinded, central Statistician. The patients will be told, within the informed consent document, of the existence of a placebo arm.

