50%	10%	80%	40
55%	10%	80%	32

The ONSTIM (occipital nerve stimulator) study (Saper et al.) recorded a placebo (preset stimulation) efficacy of 6% and a responder rate (reduction of 50% or more in headache frequency) of 39%. Results from the PREMICE study (Cefaly, supraorbital transcutaneous neurostimulation) cited by Lambert listed a placebo efficacy of 12.1% and a responder rate of 37%. Both studies evaluated between 60-70 patients. Therefore, the range of 10-15% for placebo efficacy is felt to be relatively conservative as compared with other recent studies involving neuromodulation devices addressing Migraine Headache. The assumed efficacy rate range for the CVS Device is based on non-statistically significant observations in the two previous Migraine pilot studies. We therefore conclude that a total Study size of 80 patients is likely to be sufficient for the most probable outcomes, as that number exceeds the minimum in the table above for the most likely treatment and placebo efficacy cases. For comparison, Topiramate (Topamax) used as a prophylactic migraine treatment reports responder rates in the 37-54% range and a placebo response in the low 20% range. Therefore CVS-M responder rates in the 45-55% range would be clinically meaningful.

• **Cohort size**: Each of the sites will enroll subjects with an overall goal of 80 patients. Once up to 80 subjects have completed the Pivotal Study successfully, enrollment in the Pivotal Study will be stopped (at least temporarily) and the data will be analyzed and summarized. Using expected levels of efficacy for the Treatment and Placebo Devices, this cohort size will likely be more than adequate to demonstrate statistical significance and reject the null hypothesis. The cohort size is also expected to be adequate to establish the low rate of unanticipated adverse events associated with usage of the Device. The Sponsor may choose to extend the Study, with IRB approval, should it be necessary to increase the patient cohort size.

Summary of analytical methodologies to be used for additional safety assessments and for the Secondary Endpoints:

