- **Treated Headache:** A Migraine Headache lasting at least 30 minutes for which a patient takes an acute abortive medication.
- **Treatment Device** shall mean a SNS CVS-M Device that is fully active and functioning.
- **Treatment Period** shall mean, with respect to each Pivotal Study participant, the three months following the end of the pre-Treatment Baseline Period. The third Month of the Treatment Period shall be the primary period for which efficacy of the SNS CVS-M Device treatments shall be evaluated.
- Vestibular System Consultant will be [name]., U. of Pittsburgh Medical Center, Dept. of Otolaryngology, Pittsburgh, PA.
- Vestibular Testing Procedure shall consist of the administration of the Berg Balance test. The test results will be reviewed by the Vestibular System Consultant (who will remain blinded).

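### No analysis set and no rule for a missing Month 3: patients who leave early would most likely drop out of the headache endpoints

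*Combined protocol and SAP*

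**What the plan says.** Section 3 (Pivotal Study Size; Randomization) sets the size as "enrolling up to eighty (80) patients who will successfully follow through to completion of their participation in the Pivotal Study". Section 9 (Cohort size) repeats this as a stopping rule: "Once up to 80 subjects have completed the Pivotal Study successfully, enrollment in the Pivotal Study will be stopped". Neither place says what makes a completion successful, and neither fixes the number randomised.

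The efficacy window is narrow. The Background says that "only the Headache burden during the last Month will be used for comparison with baseline data", and the definition of Treatment Period adds: "The third Month of the Treatment Period shall be the primary period for which efficacy". Section 7 puts the headache endpoints (Migraine Headache Days, 50% response, Total Monthly Headache Pain, Treated Headaches) in that month.

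The Withdrawal Criteria in section 2 open with "Subjects must be withdrawn from the clinical trial if any of the following events occur". The list includes "The subject is unwilling to continue due to lack of efficacy", and also the sponsor having reached its targeted enrolment. After discontinuation, "the Investigator must make every effort to perform all evaluations for the final visit". Continued diary entry is not mentioned.

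The nearest text to an analysis population is in section 9, where the blinded Statistician is to "analyze and summarize the Daily Headache Diaries for all patients". Section 8 says that pain totals are calculated for each subject. No section names an analysis set, a rule for a missing or partial Month 3, an imputation method or a sensitivity analysis.

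**The concern.** A patient who leaves in Month 1 or 2 has no 28-day Month-3 count, and the plan does not say how to score that patient. One listed reason for leaving is itself a poor outcome, so the missing counts may not be a random sample.

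Two comparisons are exposed in different ways. The primary endpoint in section 7 compares the active arm with its own baseline. If poor responders leave that arm, the remaining mean improves whatever happens on placebo. The chi-square in section 9 compares arms, and its false-positive rate shifts only if outcome-related loss differs between them.

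The Quality of Life and Cognition endpoint is outside this point, because the final visit can supply it.

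**Working it through.** **Inputs from the documents.** Response is a reduction of at least 50% in Migraine Headache Days. Placebo response is 10–15% and active 45–55%. The test is a two-sided Pearson chi-square at 80% power with 1:1 allocation, and 80 completers are planned (40 per arm). Alpha is not stated, so 0.05 is assumed.

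**Inputs assumed.** The documents give no withdrawal rate. I use 10%, 20% and 30%.

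**1. The plan's own table.** Per arm, n = [1.96√(2p̄(1−p̄)) + 0.842√(p1(1−p1)+p2(1−p2))]² / (p1−p2)². For 45% v 15%: (1.270 + 0.515)² / 0.09 = 35.4, so 36 per arm and 72 in total. The six rows come out as 72, 54, 44, 50, 40 and 32, all as printed and with no withdrawal allowance. So 80 works as a count of evaluable completers. Exact power at 40 per arm for 45% v 15% is 85%.

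**2. Response among completers.** Let r be the true response, w the share of non-responders who leave, and f the responders' leaving rate relative to w (0 = only non-responders leave, 0.5 = half rate, 1 = unrelated to response).

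Completer response = r(1−fw) / [r(1−fw) + (1−r)(1−w)].

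For r = 0.15 and f = 0: w = 0.30 gives 0.15/0.745 = 0.201, and w = 0.10 gives 0.15/0.915 = 0.164. For f = 0.5: 0.1275/0.7225 = 0.176 and 0.1425/0.9075 = 0.157.

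**3. False positives favouring active.** There is no true effect, r = 15%, and 40 complete per arm. The method is exact binomial enumeration of the uncorrected chi-square.

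| w, active/placebo | only non-responders leave | half rate | unrelated |
|---|---|---|---|
| none | 2.7% | 2.7% | 2.7% |
| 20%/20% | 2.6% | 2.6% | 2.7% |
| 20%/10% | 4.0% | 3.3% | 2.7% |
| 30%/10% | 6.4% | 4.35% | 2.7% |
| 10%/30% | 0.9% | 1.5% | 2.7% |

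At 10% response, 30%/10% gives 6.0% (half rate 4.4%) against 2.9% with no loss.

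**4. Power if the device works (45% v 15%).** Loss of 10%/30% cuts completer power from 85% to 75% (half rate 80%).

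**5. Within the active arm.** Losing 30% of non-responders turns 15% response into 20% (half rate 18%) and 45% into 54% (half rate 50%). For the mean change in Migraine Headache Days, assume normal changes, no true effect, and w applied to those who did not improve. The shift in SD is √(2/π) × [(1−w)−(1−fw)] / [(1−w)+(1−fw)]. With w = 0.30 and f = 0 this is 0.798 × (−0.30/1.70) = −0.14 (half rate −0.08). With w = 0.20 it is −0.09 (half rate −0.05). The sign is toward a reduction, and the placebo arm plays no part.

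**6. Counting missing as non-response, checked in the same way.** Assume 48 randomised per arm and no true effect. The response rate becomes 0.15(1−fw).

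| w, active/placebo | model | completers only | non-responder counting |
|---|---|---|---|
| 30%/10% | only non-responders leave | 6.6% | 2.8% |
| 30%/10% | half rate | 4.4% | 1.7% |
| 10%/30% | half rate (0.1425 v 0.1275) | 1.4% | 4.5% |
| 10%/30% | unrelated (0.135 v 0.105) | 2.3% | 7.2% |

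Neither rule is free of bias once loss is unequal.

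**The case against.** Recruiting until 80 complete is a rule about enrolment, and it is compatible with analysing everyone randomised. The wording about all patients and each subject points that way. The inclusion criteria expect the diary to run to the end of the study, and the test-procedures table in section 12 speaks in one case of withdrawal from the treatment phase only. So a reader who infers that the plan prescribes a completers analysis goes beyond the text. That part of the objection stands. It does not close the gap: none of these passages gives an early leaver a Month-3 count or says how to score one.

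A reader might also infer that the chi-square is biased in favour of the device. The documents do not support that. They give no withdrawal rates. Leaving for lack of efficacy should be equal across arms if the device does nothing, and heavier on placebo if it works, which counts against the device. Equal loss cannot be presumed either: active sessions last about 19 minutes against about 4 on placebo, and transient nausea or minor dizziness is foreseen. The direction is open.

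The Statistician's blinding limits choosing an analysis by its result, but it supplies no rule and no data.

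**Conclusion.** The silence on analysis set and missing Month-3 data is certain. That early leavers would then fall out of the headache endpoints is the most likely result of following the plan, not something it states.

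The within-active-arm primary endpoint is flattered if poor responders leave, by up to 0.14 SD in the cases worked, even with equal loss across arms. For the chi-square, false positives favouring active move from 2.7% to between 0.9% and 6.4%, depending on assumed unequal, outcome-related loss. With equal loss, or loss unrelated to response, they do not rise.

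A reader might conclude that 80 is too few. That does not follow, because the table reproduces and 80 exceeds every row. A reader might also take the targeted-enrolment criterion to mean that patients still in treatment will be removed. It can be read literally that way, but the text does not settle it.

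This should be fixed, and early, because diaries not collected cannot be recovered.

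**What to change.** 1. Make all randomised patients the primary analysis set, including those still in treatment when 80 have completed. Reconcile the targeted-enrolment withdrawal criterion in section 2 with this, and define successful completion.
2. For data collection, separate stopping treatment from leaving the study. Ask patients who stop to continue the existing computer-based diary through Day 112 if they agree, and use those Month-3 data. This need not change who stops treatment.
3. State one primary rule per endpoint for Month-3 data still missing, and cover partial diaries. For Migraine Headache Days, Total Monthly Headache Pain and Treated Headaches, use a likelihood-based repeated-measures analysis of the Month 1–3 diaries. For the responder chi-square, count the patient as a non-responder. Because that rule has its own bias under unequal loss, report completers and an alternative such as multiple imputation as sensitivity analyses.
4. Report withdrawals by arm and reason.

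The cost is revised wording in the withdrawal and analysis sections, some diary follow-up, and a less favourable responder rate. With 15% withdrawal in both arms unrelated to response (assumed), 45% v 15% becomes 0.45 × 0.85 = 38% v 0.15 × 0.85 = 13%. Power is then 83% if recruitment runs to 80 completers (80/0.85, about 94 randomised), 80% with 86 randomised and 77% with 80 randomised, against 85% for 80 completers. If only non-responders leave, the rule leaves 45% v 15% unchanged and costs no power.
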